7.2.5 Sponsor Responsibility for Reporting Adverse Events

All Adverse Events will be reported to regulatory authorities, IRB/IECs and investigators in accordance with all applicable global laws and regulations, i.e., per ICH Topic E6 (R1) Guidelines for Good Clinical Practice.

7.3 TRIAL GOVERNANCE AND OVERSIGHT

Executive Oversight Committee

The Executive Oversight Committee (EOC) comprises members of Sponsor Senior Management. The EOC will receive and decide upon any recommendations made by the External Data Monitoring Committee (eDMC) regarding the trial.

7.3.1 Data Monitoring Committee

To supplement the routine trial monitoring outlined in this protocol, an external Data Monitoring Committee (eDMC) will monitor the ongoing, accumulating safety data from this trial. The voting members of the committee are external to the Sponsor. The members of the eDMC must not be involved with the trial in any other way (e.g., they cannot be trial investigators) and must have no competing interests that could affect their roles with respect to the trial.

The eDMC will make recommendations to the EOC regarding steps to ensure both subject safety and the continued ethical integrity of the trial. Also, the eDMC will review ongoing trial safety results, consider the overall risk and benefit to trial participants and recommend to the EOC if the trial should continue in accordance with the protocol. The eDMC will evaluate the accumulating available data for safety at the completion of Dose Cohort #1 for each age group, prior to each age group starting the next dosing group (Dose Cohort #2), and at other time points as determined by the study team and eDMC.

Specific details regarding composition, responsibilities, and governance, including the roles and responsibilities of the various members and the Sponsor protocol team; meeting facilitation; the trial governance structure; and requirements for and proper documentation of eDMC reports, minutes, and recommendations will be described in a separate charter that is reviewed and approved by the DMC. The eDMC will monitor the trial at an appropriate frequency, as described in the detailed eDMC charter. The eDMC will also make recommendations to the Sponsor protocol team regarding steps to ensure both subject safety and the continued ethical integrity of the trial.

8.0 STATISTICAL ANALYSIS PLAN

8.1 Statistical Analysis Plan Summary

This section contains a brief summary of the statistical analyses for this trial. Full detail is in the Statistical Analysis Plan (SAP) (Section 8.2).

This section outlines the statistical analysis strategy and procedures for the study. If, after the study has begun, changes are made to primary and/or key secondary hypotheses, or the statistical methods related to those hypotheses, then the protocol will be amended (consistent with ICH Guideline E-9). Changes to exploratory or other non-confirmatory analyses made after the protocol has been finalized, along with an explanation as to when and why they occurred, will be listed in the Clinical Study Report (CSR) for the study. Post hoc exploratory analyses will be clearly identified in the CSR. No separate Statistical Analysis Plan (SAP) will be issued for this study.

8.1.1 Pharmacokinetic Analyses

The primary PK population for POS IV solution will be all treated subjects who receive at least 7 days of POS IV solution therapy and complete the full POS PK sampling while on POS IV solution. The non-compartmental PK analysis will be used for the primary PK population.

For POS PFS therapy, a population PK analysis will be conducted to determine the individual PK exposure since sparse PK samples will be collected for patients who are outpatients during the POS PFS treatment period. Model-predicted individual concentration-time profiles will be used to determine C_{\max} , C_{\min} , C_{avg} , and AUC.

PK parameters (C_{\max} , T_{\max} , C_{\min} , C_{avg} , AUC, CL and CL/F) for both POS IV solution and POS PFS will be summarized using descriptive statistics as described in Section 8.2.1 below.

A non-compartmental PK analysis will be performed to determine the PK exposure of sulfobutylether-beta-cyclodextrin-containing (SBE β CD).

8.1.2 Safety Analyses

The All-Subjects-as-Treated (ASaT) population will be employed for safety analyses, and consists of all subjects who took at least one dose of POS study therapy.

8.1.3 Efficacy Analyses

There are no efficacy analyses planned for this study.

8.1.4 Power and Sample Size

A total of approximately 120 subjects will be screened to obtain a minimum of 72 PK-evaluable subjects in the PK analysis.

8.2 Statistical Analysis Plan

8.2.1 Pharmacokinetic Analysis Plan

Only subjects who receive at least 7 days of POS IV solution therapy and complete the full POS PK sampling while on POS IV solution will be included in the non-compartmental PK analysis for the primary patient population.

PK parameters for POS (C_{max} , C_{min} , C_{avg} , CL) will be listed and summarized by POS formulation, dose cohort, and age group using descriptive statistics.

For POS PFS therapy, a population PK analysis will be conducted to determine the individual PK exposure. A population PK model will be developed using the plasma data collected from this study in combination with the adult PK data. Model-predicted individual concentration-time profiles will be used to determine C_{max} , C_{min} , C_{avg} , AUC and CL/F for patients receiving POS PFS. Covariates of age group and dose cohort will be explored in the model.

Comparison of the exposure from previous experience in adults (from P05520 for the POS IV formulation; P05615 for the tablet formulation) will be conducted at steady state using graphics. Additionally, the proportion of subjects in PN097 with steady-state C_{avg} greater than or equal to 500 ng/mL (as well as the proportion of subjects with C_{avg} between 500-2500 ng/mL) will be compared to the previous studies using descriptive statistics.

A non-compartmental PK analysis will be performed to determine the PK exposure of sulfobutylether-beta-cyclodextrin-containing (SBE β CD). PK parameters for POS (C_{max} , T_{max} and AUC) will be listed and summarized by POS dose cohort, and age group using descriptive statistics.

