4.2.2 Rationale for Dose Selection/Regimen

Rationale for dose cohorts 1 and 2 included in original protocol version, MK-5592-097-00

The starting dose of 3.5 mg/kg/day for the POS IV solution and POS PFS formulation was projected via modeling and simulation to achieve the pharmacokinetic (PK) target of an average concentration (C_{avg}) of between 500 and 2500 ng/mL in approximately 90% of patients 2 to 17 years of age (see Section 4.2.3 for details regarding the PK target). In this

study, if at least 10 out of 12 PK-evaluable patients in a dose cohort achieve a C_{avg} in the specified range the PK exposure target will be considered to have been met.

Specifically, utilizing population PK models developed for the POS IV solution and the POS PFS formulation based on observed adult PK data, simulations were conducted to project the exposure in the pediatric population. The PK profile of the POS PFS formulation is expected to be comparable to the POS tablet, based on results of a biocomparison study conducted in adults. The PK concentration versus time profile in the pediatric population was projected by allometrically scaling model parameters by body weight, and simulating the resulting profiles, then calculating the distribution of projected C_{avg} values for each formulation for young children (2 to <7 years) and adolescents (7 to 17 years).

For the POS IV solution, a dose of 3.5 mg/kg/day was expected to result in 91% of young children (2 to <7 years) and 96% of adolescents/older children (7 to 17 years) with C_{avg} values within the target range of 500 and 2500 ng/mL. For the POS PFS formulation, 85% of young children (2 to <7 years) and 90% of adolescents (7 to 17 years) were expected to achieve the PK target.

For the POS IV solution, a dose of 4.5 mg/kg/day was expected to result in 94% of young children (2 to <7 years) and 88% of adolescents/older children (7 to 17 years) with C_{avg} values within the target range of 500 and 2500 ng/mL. For the POS PFS formulation, 90% of young children (2 to <7 years) and 86% of adolescents/older children (7 to 17 years) were expected to achieve the PK target.

Rationale for the addition of third dose cohort (6 mg/kg) in Amendment MK-5592-097-02

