4.2.4.3 Pharmacokinetic Endpoints

The primary endpoint will be C_{avg} for both the POS IV solution and POS PFS. The C_{avg} will be calculated by dividing the AUC with dosing interval. Additionally, C_{min} , C_{max} , T_{max} , and AUC will also be calculated for patients in each age group per dose cohort.

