- e. For inpatients, perform focused physical exam and record vital signs 2 times per week, at least 2 days apart while on POS PFS. For outpatients, perform focused physical exam, and record vital signs once per week while on POS PFS.
- f. The subject's weight as measured within 3 days prior to the first dose of oral treatment (PFS) will be used to calculate the first and all subsequent doses of PFS.
- g. ECG may be performed on Day 8, 9, or 10 of PFS
- h. Hematology: complete blood count (CBC) with differential; Serum Chemistry: BUN, calcium, serum creatinine, potassium, sodium, glucose, AST, ALT, alkaline phosphatase, total bilirubin, albumin, total protein, magnesium, chloride, and bicarbonate. The first sample after the first day of POS PFS should be collected no later than the 5th dose of POS PFS.
- i. For inpatients, hematology and chemistry testing must be performed 2 times per week with at least 2 days in between samples. For outpatients, lab testing must be performed once per week while on POS PFS
- j. ANC must be drawn a minimum of twice a week for inpatients and once per week for outpatients while on POS PFS and during periods of neutropenia (ANC <500/mm³). The first sample after the first day of POS PFS should be collected no later than the 5th dose of POS PFS.
- k. **POS plasma trough sampling** during POS PFS administration (0.35 mL of blood per sample): Collect trough sample pre-dose (0 hr) on the 6th day of POS PFS and at the end of POS therapy. For premature discontinuations, a trough level sample will be taken approximately 24 hours after administration of the last dose, and all other safety assessments will be performed according to the Last Day of POS PFS schedule. The trough may be collected at either the 5th or 6th day of POS PFS to coincide with other labs.
- l. For subjects continuing for more than 7 days of POS PFS treatment, POS trough samples should be collected once per week with other required labs.
- m. **PK full sampling during POS PFS administration** (0.35 mL of blood per sample): If an inpatient, perform PK sampling at pre-dose (0 hour), and 2, 4, 6, 8, and 24 hours post-dose; if an outpatient, perform PK sampling at predose (0 hour) 2, and 4 hours post-dose. Full PK sampling may be performed anytime between the 7th through the 10th day of POS PFS treatment.

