7.1.2.2 Body Weight (kg)

Body weight at Baseline will be used to calculate the subject's dose for the IV treatment phase of the study. The subject's weight measured within three days prior to the first dose of oral treatment should be used to calculate all oral treatment (PFS) doses. The actual weight measured should be recorded. Body weight should be obtained without shoes. At each required visit, it is preferred that the weight should be measured on the same scale for the same individual. Measurements should be recorded to the nearest tenth of a kg.

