7.1.3.2 Pharmacokinetic/Pharmacodynamic Evaluations

Plasma posaconazole concentration data will be used to estimate the following PK parameters:

- C_{avg} : Average steady-state plasma concentration
- C_{min} : POS trough level immediately before a subject receives the dose on the day specified in the protocol
- C_{max} : Maximum plasma concentration
- T_{max} : Time of maximum plasma concentration
- AUC: Area under the plasma concentration versus time curve
- CL: Total body clearance
- CL/F: Apparent total body clearance

The current blood sampling schedule is an optimized schedule based on the adult steady-state PK data. For patients receiving IV therapy, if all blood samples can be collected at steady-state as scheduled, the steady-state AUC will be calculated using the non-compartmental trapezoidal method. The C_{avg} will be calculated by dividing the AUC with dosing interval. For patient receiving PFS, since sparse PK samples are collected for outpatients, a population PK analysis will be conducted and model-predicted plasma concentration-time profiles will be used to determine C_{avg} .

Plasma sulfobutylether-beta-cyclodextrin-containing (SBE β CD) concentration data will be used to estimate the following PK parameters:

- C_{max} : Maximum plasma concentration
- T_{max} : Time of maximum plasma concentration
- AUC: Area under the plasma concentration versus time curve

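### Does Section 8.2.1 need to say how body weight enters the population PK model behind oral (PFS) Cavg?

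*Combined protocol and SAP*

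**What the plan says.** Section 4.2.4.3 makes Cavg the primary endpoint "for both the POS IV solution and POS PFS". For IV, Sections 7.1.3.2 and 8.1.1 use non-compartmental analysis. For PFS, Section 7.1.3.2 gives the reason for a model: "since sparse PK samples are collected for outpatients, a population PK analysis will be conducted and model-predicted plasma concentration-time profiles" supply Cavg. The sparse schedule is in the Section 6.2 footnotes: "if an outpatient, perform PK sampling at predose (0 hour) 2, and 4 hours post-dose". Inpatients give samples at 0, 2, 4, 6, 8 and 24 h.

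Section 8.2.1 describes the model in two sentences: "A population PK model will be developed using the plasma data collected from this study in combination with the adult PK data", and "Covariates of age group and dose cohort will be explored in the model". Section 8.1 adds: "No separate Statistical Analysis Plan (SAP) will be issued for this study".

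Weight appears elsewhere. In Section 4.2.2 the paediatric profiles behind the first doses were "projected by allometrically scaling model parameters by body weight". In Section 7.1.2.2 the "weight measured within three days prior to the first dose of oral treatment should be used to calculate all oral treatment (PFS) doses".

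**The concern.** The model alone produces a primary endpoint, the protocol is the only analysis plan, and the two covariates it names omit the one that drives dosing. A two-level age factor cannot carry weight from a 2-year-old to an adult.

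The possible error looks large at first. At 6 mg/kg, a 15 kg child gets 90 mg and a 50 kg child 300 mg. If clearance ignored weight, the ratio of their expected Cavg would be 90/300 = 0.30. If clearance rises with weight to the power 0.75 (assumed), it is 0.30^0.25 = 0.74. For a child with few samples, the individual prediction is pulled toward whatever the model expects.

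The second worry is comparability. In the interim Tables 1 and 2, a predose value replaced a missing 24 h sample so that Cavg could be calculated, which suggests direct calculation from observed profiles. If the final PFS values come from a model, they may differ by method from those tables and from IV, and no side-by-side table is planned.

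**Working it through.** **1. The plan's own figures.** The only computed probability that uses Cavg is the chance of at least 10 of 12 successes at p = 0.90 (Section 8.2.5): 0.9^12 + 12(0.9^11)(0.1) + 66(0.9^10)(0.01) = 0.282 + 0.377 + 0.230 = 0.889, as stated. In Table 2 the PFS values of AUC/24 are 512.5, 862.5, 975 and 1196, against printed Cavg of 511, 861, 976 and 1190. All agree within 0.5%. This shows that Cavg is AUC over 24 h; it does not show whether AUC was observed or modelled.

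**2. How much true exposure varies with weight.** Take Cavg proportional to min(6W, 300)/W^0.75 (exponent and weights assumed).

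| Weights compared | Ratio of Cavg |
|---|---|
| 50 vs 22 kg | 1.228 |
| 24 vs 12 kg | 1.189 |
| 70 vs 15 kg | 1.050 |
| 65 vs 22 kg | 1.009 |

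Per-kg dosing with a cap keeps the expected range modest.

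**3. What omitting weight would do to individual values.** The simulation uses a one-compartment oral model with outpatient samples at 0, 2 and 4 h, 6 mg/kg capped, run within each age group. Every PK value is assumed: CL/F 9.23 L/h and V/F 221 L at 70 kg, ka 0.4/h, between-subject SDs 0.4, 0.3 and 0.5, N = 1200.

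| Age group (weights) | Residual CV | Omitted: lightest / heaviest third | Included: lightest / heaviest third | In-range share: included vs omitted |
|---|---|---|---|---|
| 2 (22-70 kg) | 25% | -5.7% / +6.8% | 0.0% / +0.2% | 0.889 vs 0.881 |
| 2 (22-70 kg) | 40% | -8.8% / +8.9% | -0.6% / -0.9% | 0.902 vs 0.883 |
| 1 (12-24 kg) | 25% | -4.2% / +5.3% | +0.2% / +0.4% | 0.941 vs 0.937 |
| 1 (12-24 kg) | 40% | -6.6% / +6.0% | -0.4% / -0.8% | 0.953 vs 0.942 |

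Repeat runs under the same assumed PK values widen the errors with weight omitted to about -3 to -11% and +2 to +9%. Bias in the whole-age-group geometric mean stays under 2% whether weight is in or out.

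**4. The same question at the plan's predicted exposure.** For Age Group 1 on PFS, Section 4.2.2 predicts a geometric mean of 847 ng/mL with 83.5% in range. A log-normal fit gives SD 0.506 on the log scale. The 500 limit is then at z = ln(500/847)/0.506 = -1.04, where the density is 0.232/0.506 = 0.458 per log unit. Lowering the lightest third by 11% moves 0.458 x 0.1165/3 = 1.8 points below 500. Raising the heaviest third by 9% returns 0.458 x 0.0862/3 = 1.3 points. The net change is about half a point.

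**5. What the plan reports.** Section 8.2.1 summarises by formulation, dose cohort and age group, and compares the shares at or above 500 and in 500-2500 ng/mL with adult studies descriptively. No summary by weight band is planned, and that is the only place where the errors in step 3 would show.

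**6. Method across cohorts.** Section 8.2.1 fits this study's plasma data and takes Cavg from the model for patients on PFS, with no restriction to Dose Cohort #3. In the final analysis all three cohorts therefore share one method. IV and PFS are to be assessed separately within each cohort (Section 2.1), so their difference in method disturbs no planned contrast.

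**The case for a change.** The strongest reply is that a plan which lists covariates and leaves out weight invites a reader to take the list as complete, and that naming weight would cost a sentence. The first half is fair as a criticism of drafting. But the wording says two covariates will be explored; it does not say that structural scaling is dropped, and a modeller pooling 2-year-olds with adults would scale by weight, as the projections from adult data did.

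A second reply concerns shrinkage. Predicted attainment on PFS at 6 mg/kg is 83.5% and 82%, close to 10/12 = 83.3%. Sparse profiles pull individual estimates toward the centre, and an assumed 20% reduction in SD would lift these shares to 90.0% and 90.6%. This stands as a caution in reading the results. The documents give no shrinkage figure, however, and the effect comes from sparse sampling with or without weight in the model. Dose Cohort #3 is also the last cohort (Section 4.2.2.2) with no formal interim analysis (Section 8.2.6), so no further escalation in this trial depends on that share.

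A third reply is that non-compartmental PFS values are feasible. They are, for some subjects: interim PFS cells held 5, 10, 7 and 8, and 30 PFS against 57 IV subjects (53%) suggests about 13 to 19 among 24 to 36 in Dose Cohort #3. Such a table would cover the fully sampled subjects only, some with a carried-over 24 h value. It would help link to the interim tables but would alter no planned result.

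**Conclusion.** No change to the plan is needed. The omission is real, but it is modelling detail that analysts fill sensibly, with the weight data and the precedent both in the protocol. If weight were nevertheless left out, individual PFS Cavg would be misstated by roughly 3 to 11% in the outer weight thirds of an age group. The planned summaries would hold: bias in the geometric mean under 2%, and the in-range share changed by 2 points or less.

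These sizes rest on assumed clearance, variances, weights and an exponent of 0.75, and on a model centred within each age group, which the age-group covariate allows. The simulation is on the pessimistic side, because it uses three oral samples only. PFS subjects also have troughs and an earlier scheduled six-sample IV profile; adding the IV profile cut the errors in the weight thirds from about 3-8% to about 2-5%, if the final model is fitted jointly, which the plan does not state. The study is descriptive and has no formal power calculation, so no test result is at risk. Only a comparison of final PFS values with the interim Tables 1 and 2 could mix methods, and those tables served the earlier escalation decision.

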8.2.2 Safety Analyses

All subjects who receive at least one dose of study drug will be included in the safety analysis.

Adverse events (AEs) will be tabulated by age (2 to <7 years, 7 to 17 years) and POS treatment (IV solution, PFS). The number and percent of each event will be computed and summarized by body system organ class. Severity, duration, relationship to POS, and outcome of the events will also be recorded. ECGs and clinical safety laboratory values, such as hematology and serum chemistry, will be tabulated by age and treatment group and compared to baseline using summary statistics. Vital signs will be listed by date and time. Key toxicities, including hepatotoxicity and nephrotoxicity, will be tabulated by age and dose cohorts.

Additionally, survival at Day 100 (allowed range Day 90 -110) and Day 65 (allowed range Day 60-70) will be tabulated by age group and dose cohort.

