1.0; 2.1; 8.2.5	Trial Summary; Trial Design; Power and Sample Size	Addition of 36 subjects to the study to be enrolled in the newly added third dose cohort (6 mg/kg).	The number of subjects enrolled in this cohort is being increased from a minimum of 24 subjects, as was enrolled in the initial two dose cohorts, to a minimum of 36 in order to generate a more robust safety database at the likely dose that will achieve sufficient PK exposures.
-----------------------	--	---	---

ADDITIONAL CHANGE(S) FOR THIS AMENDMENT:

Section Number(s)	Section Title (s)	Description of Change (s)	Rationale
Note: a few grammar edits were included throughout the protocol to enhance readability.			
4.2.2.2	Maximum Dose/Exposure for This Trial	Additional description of 300 mg/day as maximum dose.	Clarification of reasoning of the maximum dose choice.
5.1.2	Subject Inclusion Criteria	The following text was deleted from inclusion criterion #5: "Sexually active females of childbearing potential must have a negative urine pregnancy test which must be followed up with a confirmed negative serum pregnancy test (β -HCG) within 48 hours following the screening visit."	A serum pregnancy test is no longer required at Screening. Pregnancy is listed as an exclusion criterion, and details of serum and urine test requirements are now clarified in Section 6.1, Trial Flow Chart Part 1, footnote e, and in Section 7.1.3, Laboratory Procedures/Assessments.

6.1 (Part 1)	Trial Flow Chart Part 1: (Visits 1-14)	Footnote e, addition of the following language: If a serum pregnancy test is performed at screening and the baseline visit occurs more than 2 days after screening, the serum pregnancy test should be repeated at the baseline visit. If the baseline visit occurs 2 days or less from the screening visit, serum pregnancy test is sufficient and a pregnancy test does not need to be repeated at the baseline visit. A urine pregnancy test may be substituted for a serum pregnancy test at the screening visit; however, if a urine pregnancy test is used for screening, it must be followed up with a confirmed negative serum pregnancy test within 48 hours.	To provide clarification of pregnancy testing requirements at screening and baseline visits. And to clarify that negative serum pregnancy test results are required before treatment.

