3.2 Secondary Objective(s) & Hypothesis(es)

- 1) **Objective:** To evaluate the safety and tolerability of POS IV solution and POS PFS administered to immunocompromised pediatric subjects (ages 2 years to 17 years) with neutropenia or expected neutropenia

Estimation: Safety parameters will be summarized for each age group and dose cohort.

3.3 Exploratory Objectives:

- 1) **Objective:** To evaluate the palatability and acceptability of POS PFS
- 2) **Objective:** To evaluate the PK of sulfobutylether-beta-cyclodextrin (SBE β CD)

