8.2.5 Power and Sample Size

The sample size is not based on any formal power calculation.

The total sample size for the study is a minimum of 84 subjects (72 PK-evaluable subjects) distributed across the 3 dose cohorts as follows:

Dose cohort #1 (a minimum of 24 PK evaluable subjects, divided 12 per Age Group).

Dose cohort #2 (a minimum of 24 PK evaluable subjects, divided 12 per Age Group).

Dose cohort #3 (a minimum of 36 subjects, divided as 12 PK evaluable subjects per Age Group and an additional 12 distributed across either Age Group).

The actual total number of enrolled subjects may be greater than 84 in order to ensure a minimum of 72 subjects that meet PK evaluability criteria.

At the time of this amendment (MK-5592-097-02), enrollment in Dose Cohorts #1 and #2 is complete. Therefore, the remaining target enrollment for this amendment is a minimum 36 subjects in Dose Cohort #3 (12 PK evaluable subjects per age group and an additional 12 distributed across either age group).

If successful dose selection is defined as at least 10 out of 12 (82.2%) patients per age/dose group achieving a $C_{avg} > 500$ ng/mL, the chance of achieving success is at least 89%, based on a sample size of 12 patients in each age/dose cohort using a binomial distribution ($n=12$, $p=0.90$), where p = probability of success.

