8.2.6 Interim Analysis

Interim Analysis for Dose Cohorts #1 and #2

For the 2 dose cohorts (3.5 mg/kg and 4.5mg/kg) which have completed enrollment at the time of this amendment, a pre-planned interim summary of PK and safety data was conducted in order to inform the decision to advance to the next higher dose cohort. Because these data summaries did not involve formal tests of hypotheses, they did not affect type I error.

Interim Analysis for Dose Cohort #3

There is no formal interim analysis planned for the third dose cohort (6 mg/kg).

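### The adverse event tabulation in 8.2.2 leaves out dose cohort, which the secondary objective in 3.2 requires

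*Combined protocol and SAP*

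**What the plan says.** The secondary objective (3.2) is the safety and tolerability of both formulations, the IV solution and the powder for oral suspension (PFS). Its estimation statement reads: "Safety parameters will be summarized for each age group and dose cohort".

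Section 8.2.2 gives the layout of the general AE table: "Adverse events (AEs) will be tabulated by age (2 to <7 years, 7 to 17 years) and POS treatment (IV solution, PFS"). Counts and percentages then follow by body system. In the same section, "Key toxicities, including hepatotoxicity and nephrotoxicity, will be tabulated by age and dose cohorts", and survival is also by age group and dose cohort. ECG and laboratory values are by age and 'treatment group', a term that 8.2.2 does not define. Section 8.2.4 uses the same term for compliance and palatability.

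For PK, 8.2.1 uses all three factors: parameters "will be listed and summarized by POS formulation, dose cohort, and age group using descriptive statistics".

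Section 8.1 states: "No separate Statistical Analysis Plan (SAP) will be issued for this study". Section 8.1.2 names the safety population and gives no layout.

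Dose Cohort #3 is planned as "a minimum of 36 subjects, divided as 12 PK evaluable subjects per Age Group and an additional 12 distributed across either Age Group" (8.2.5). The Summary of Changes gives the reason for enlarging it: "in order to generate a more robust safety database at the likely dose that will achieve sufficient PK exposures".

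**The concern.** This is a sequential dose-escalation trial, and the only analysis text for its general AE table omits dose. The objective and the analysis meant to serve it state different layouts. The SAP names dose cohort elsewhere when that split is wanted, so a programmer following 8.2.2 would have reason to leave it out.

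The stake is mainly the 6 mg/kg cohort. For Cohorts #1 and #2, "a pre-planned interim summary of PK and safety data was conducted" (8.2.6). No formal interim analysis is planned for Cohort #3. Section 7.3.1 fixes data monitoring committee reviews only around the step from Cohort #1 to Cohort #2 and leaves any others to discretion. Apart from such discretionary reviews, the final tables are where the general AE profile at 6 mg/kg would be seen. Followed literally, 8.2.2 would show that profile only mixed with two lower doses.

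**Working it through.** No figure stated in the plan bears on this point. The check is a comparison of layouts, followed by an illustration of what pooling does.

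**Layouts**

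| Output | Age | Dose cohort | Formulation |
|---|---|---|---|
| Safety parameters, 3.2 | yes | yes | not in the estimation statement |
| General AEs, 8.2.2 | yes | no | yes |
| Key toxicities and survival, 8.2.2 | yes | yes | no |
| ECG and laboratory, 8.2.2 | yes | unclear ('treatment group') | unclear |
| PK parameters, 8.2.1 | yes | yes | yes |

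The AE table in 8.2.2 has 2 ages × 2 formulations = 4 cells, each pooling three doses. The layout in 3.2 has 2 ages × 3 cohorts = 6 cells. Using all three factors gives 2 × 3 × 2 = 12.

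**Effect of pooling (illustration, no event rate assumed)**

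Let f be the share of subjects in a pooled row who received 6 mg/kg, p6 their AE rate, and pL the weighted average rate at 3.5 and 4.5 mg/kg. Then

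pooled rate = (1 − f) × pL + f × p6 = pL + f × (p6 − pL).

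An excess of D points at 6 mg/kg therefore appears as f × D, and the fraction 1 − f is averaged out.

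Inputs for the IV rows:
- Cohorts #1 and #2: PK-evaluable IV counts from Table 1 (4.2.2). Age Group 1 has 11 + 13 = 24, and Age Group 2 has 19 + 14 = 33.
- Cohort #3: planned minimum of 12 per age group plus 12 subjects of either age (8.2.5), so 12 to 24 per age group, or 18 with an even split.

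| | 12 at 6 mg/kg | 18 (even split) | 24 at 6 mg/kg |
|---|---|---|---|
| Age Group 1, f | 12/36 = 33% | 18/42 = 43% | 24/48 = 50% |
| Age Group 2, f | 12/45 = 27% | 18/51 = 35% | 24/57 = 42% |

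The fraction averaged out runs from 1 − 0.500 = 50% to 1 − 0.267 = 73%.

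**What a cohort-specific column could show**

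For an AE seen in none of n subjects, the one-sided 95% upper limit is 1 − 0.05^(1/n):
- n = 12: 22.1%
- n = 24: 11.7%
- n = 36: 8.0%

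The first two apply to one age group within Cohort #3 at planned minimums. The third applies only to a column combining both age groups.

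**The case against.** The strongest reply is that 3.2 and 8.2.2 belong to one document and 3.2 is equally binding. Section 8.2.2 does not say that AEs are tabulated only by age and formulation. Section 4.2.1 and the notes to Table 5 also speak of safety by dose level or cohort. On this view the AE sentence is incomplete, and nobody planned a pooled analysis. Much of this stands: the documents do not show an intention to pool, although the two latter passages may describe escalation review. It does not remove the conflict, because one text must be chosen when the table is built, and the more specific one omits dose.

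It is also fair that the tabulation is descriptive, that no final decision rule uses it, and that 8.1 lets changes to non-confirmatory analyses be recorded in the study report. These points limit the severity. A split added at that stage would still be missing from the only SAP although 3.2 promises it.

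Four stronger readings are not supported:
- **That safety as a whole is pooled over dose.** Key toxicities, an open list that names hepatotoxicity and nephrotoxicity, and survival are by cohort.
- **That 'treatment group' means dose cohort and should be replaced by it.** The Trial Summary applies the term to the age groups. Compliance in 8.2.4 spans the IV and oral phases (7.1.1.8), so formulation is also a possible meaning.
- **That formulation should give way to dose.** The objective in 3.2 covers both formulations.
- **That 50% to 73% is a bound, or that an 8.0% limit is lost.** The range joins PK-evaluable counts to planned minimums, whereas the AE table covers all treated subjects. It also ignores the 300 mg cap, which 4.2.2 says limits the exposure increase in Age Group 2. The layout in 3.2 does not ask for the all-ages column that the 8.0% needs.

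**Conclusion.** The inconsistency is real and is confined to the general AE table. Section 3.2 calls for age group and dose cohort, 8.2.2 gives age and formulation, and no further SAP will reconcile them. Followed literally, 8.2.2 leaves the enlarged 6 mg/kg cohort without a general AE column.

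The size of the effect can only be illustrated. With Table 1 IV counts and planned minimums, roughly half to three quarters of any excess at 6 mg/kg would be averaged out. Actual treated numbers could move this either way. Even with the split, cells of 12 to 24 subjects would rarely establish a dose relation. This is a minor to moderate correction to descriptive output.

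**What to change.** Amend the AE sentence in 8.2.2 so that AEs are tabulated by age group, dose cohort and POS treatment (IV solution, PFS). This satisfies 3.2, keeps formulation and matches the PK layout in 8.2.1. A total per dose cohort across age groups is an optional, low-cost addition that would give 6 mg/kg a column of at least 36 subjects.

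Define 'treatment group' where 8.2.2 and 8.2.4 use it. The sponsor should state which meaning was intended.

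The cost is wording and extra columns. No new data are needed, since each subject's cohort is known. The drawback is small denominators. At planned minimums there are 12 to 24 subjects per age group and cohort on IV. PFS cells would be smaller: the PK-evaluable PFS counts in Table 1 are 5 and 10 for Age Groups 1 and 2 in Cohort #1, and 7 and 8 in Cohort #2. Percentages in such cells should be shown with their counts.
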